Management of GI adverse effects following kidney transplantation has been established as a consistent challenge for transplant centers. Reduction of MPA immunosuppression may lead to adverse outcomes such as rejection or graft failure, and use of AZA has been associated with higher rates of graft loss. Everolimus has been studied in kidney transplant recipients, and has been shown to lead to similar rates of rejection and graft function compared to MPA. Thus, we have proposed this single-arm study to assess improvement in GI adverse effects in renal transplant recipients. If EVR demonstrates a significant benefit with regard to GI adverse effects while maintaining appropriate rejection prophylaxis, it may offer transplant a new option for patients who are experiencing such adverse effects while on MPA therapy.

We will assess patients within the first year post-transplant for signs and symptoms of GI adverse effects, and following ruling out infectious causes, they will be consented and converted to EVR at an initial dose of 1 mg PO BID, which will then be titrated to target trough goals between 3 - 8 ng/mL. Prior to drug initiation, patients will complete the GSRS and GIQLI surveys to assess for intensity of symptoms and associated quality of life. Patients will remain on study therapy for at least 12 months and GSRS and GIQLI will be repeated at 30 days, 3 months, 6 months, and 12 months.

These timelines were chosen to allow enough time to demonstrate a significant change in GSRS scores following conversion to EVR. We have chosen not to include an active control due to the added cost and time that would be required to enroll and follow the additional numbers needed. We will compare data on graft rejection, graft function, graft survival, and patient survival to an historic cohort of patients who were converted to AZA for GI adverse effects. They will be compared on a 2:1 basis to a group of randomly selected patients previously converted to AZA.

Objectives

Primary objectives

To determine if a switch from MMF or EC-MPS to Zortress (everolimus) due to GI intolerance results in improvement of GI symptoms, as measured with the GSRS survey.

Secondary objectives

To determine whether it is safe to switch from MMF or EC-MPS to Zortress (everolimus) due to GI intolerance from MMF/EC-MPS within 12 months post-renal transplantation.

[figure not shown]
Study design

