This study will be conducted over a 2-year period, during which patients will be enrolled through the first year, and follow-up of a minimum of 1 year will be collected on each patient. Interim analyses will be conducted at 6-months or upon enrollment of 15 patients (whichever is earliest). The interim analyses will assess the rate of study drug discontinuation due to non-efficacy (as determined by nephrologist). If more than 5 patients (33%) have discontinued drug due to non-efficacy, the study will be terminated. Additionally, any other problems or safety signals will be addressed by the research team at this time.

Subjects meeting criteria will be asked to sign an informed consent, and upon execution of informed consent this will be considered study day 1. They will examined on study day 1 including a medical history, medication history, vital signs, height, weight, and BMI. Subjects will complete GSRS and GIQLI surveys, report adverse effects, and complete laboratory tests, including tacrolimus levels. Subjects will have 5 additional visits during the study period, which will include a medication history, vital signs, height/weight/BMI, adverse effect recording, GSRS and GIQLI (excepting visit 5), laboratory work including tacrolimus and everolimus levels, and reporting of infectious symptoms. These visits will occur at the end of months 1, 3, 6, 9, and 12.

Figure Error! No text of specified style in document.-1 St

Study design

Population

We intend to include patients who have received kidney transplant at the Washington University/Barnes-Jewish Hospital transplant program in the year prior to enrollment who are exhibiting signs of non-infectious GI toxicity determined by the treating physician to be secondary to MPA. In total, 30 candidates will be enrolled and treated with conversion from MPA to EVR. We anticipate a dropout rate of 20%, and expect that 24 patients will complete a full year of study drug. Severity of GI adverse effects will be assessed using the GSRS and GIQLI scales, but no specific severity threshold will be used to enroll patients. The study will be conducted largely on outpatients, but patients may be initially enrolled during inpatient stays.

Inclusion criteria

Patients eligible for inclusion in this study have to fulfill all of the following criteria:

- 1. Patients must give written informed consent before any assessment is performed.

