- 2. Adult kidney transplant recipients at Washington University/Barnes-Jewish Hospital
- 3. Experiencing GI toxicity from MPA as determined by the treating physician within 12 months postrenal transplant
- 4. On standard immunosuppression with tacrolimus and prednisone

Exclusion criteria

1. Dual organ or kidney after another solid organ transplant

2. Presence of a preexisting significant GI condition that does not have a presumed causal relationship with MPA

3. Evidence of any GI disorder induced by an infection, underlying medical condition, or concomitant medication other than MPA

- 4. eGFR<35 ml/min at time of possible conversion
- 5. Proteinuria >1 gram/day at time of possible conversion
- 6. Profound bone marrow suppression at the time of possible conversion as defined as:
 - Hemoglobin <10 g/dL
 - WBC <3 K/cumm
 - Platelets <100 K/cumm

7. Wound healing issues at time of possible conversion (eg, wound dehiscence, wound infection, incisional hernia, lymphocele, seroma)

8. Elevated total cholesterol (>350 mg/dL) and/or triglycerides (>500 ng/dL) at time of possible conversion

9. Hypersensitivity to everolimus, sirolimus, or other rapamycin deriviatives

Treatment

Investigational and control drugs

Patients enrolled in the trial will receive everolimus tablets at a starting dose of 1 mg PO BID, which will be dispensed in 0.5 mg tablets in blister-packages of 60-each.

Treatment arms

This will be a single-arm study. All patients enrolled with be assigned to the everolimus arm. We will include an observational retrospective analysis of those on AZA-based immunosuppression for comparison of risk of acute rejection, chronic rejection, graft-loss, and death, but these patients have already been allocated treatment and completed follow-up.

Treatment assignment

This will be a single-arm study. All patients enrolled with be assigned to the everolimus arm.

Treatment blinding

This will be an open-label study. All participants including researchers, subjects, and analysts will be aware of treatment allocation.

Treating the patient

Patient numbering

Patients will be numbered sequentially from 1 through 30 based on the order they complete consent and enrol in the study

Dispensing the study drug

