Data collection will occur via the RedCap system. All local staff have received training on RedCap. Multiple forms will be created, including a baseline/screening form, and visit-specific forms. Only investigators will have access and the ability to download data.

Database management and quality control

The principal investigator will take responsibility for assessing quality data entry by overseeing all data entry into the RedCap system.

Data analysis (Any or all sections may be included based on type of study)

Statistical analysis and report writing will be performed when the last subject has completed 12 months on study.

Populations for analysis

Subjects completing three months of therapy and returning for study visit #2 will be included in the primary analysis. All subjects receiving at least one dose of everolimus will be included in all outcomes related to safety.

Patient demographics/other baseline characteristics

Demographic and background information for the population will be summarized using frequency distribution (for categorical variables) and descriptive statistics of mean, median, maximum, minimum and standard deviation (for continuous variables).

Treatments (study drug, rescue medication, other concomitant therapies, compliance)

The number of patients remaining on study medication at each study visit will be recorded. Additionally, mean tacrolimus and everolimus levels will be reported at each study visit.

Analysis of the primary objective(s)

Variable

The primary variable is the resultant score derived from the GSRS, which ranges from 0 - 45, compared at enrollment and at visit 2 (end of month 3).

Statistical hypothesis, model, and method of analysis

The null hypothesis: Conversion from MPA-based immunosuppression to EVR-based immunosuppression will result in similar GSRS scores at 3 months compared to baseline.

We will analyze changes in the GSRS using a paired T-test.

Handling of missing values/censoring/discontinuations

We will not include patients in the primary analysis and subsequent analyses of efficacy if they drop out of the study. We will analyze safety endpoints from a modified ITT approach, whereby patients receiving at least one dose of everolimus are considered on therapy until the end of their study period (12 months).

Supportive analyses

A per-protocol set will be analyzed as a secondary endpoint with regards to safety endpoints, including BPAR, graft loss, and death.

Analysis of secondary objectives

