Efficacy (secondary)

We will conduct analysis of GIQLI scores at visit 2, 3, 4, and 6 compared with baseline assessment, as well as inter-visit comparisons. Additionally, we will conduct subscore analyses of the GSRS and GIQLI at each of these timepoints. The pre-specified domains of the GSRS to be analyzed will be the abdominal pain, diarrhea and reflux scores. The GIQLI subscores will be analyzed for all domains.

Safety

Safety variables to be assessed include BPAR, graft loss, death, graft function at each study visit, discontinuation from study, discontinuation from treatment, infection, SAE, notable events, laboratory tests, and vital signs. All safety analyses will be done on the safety set. Selected variables will be analyzed using all available data including data assessed.

Health-related Quality of Life

As above.

Sample size calculation

The sample size was calculated based on the myTIME study. Sample size calculation showed that a minimum sample size of 25 patients will be required to provided 80% power to detect a change from baseline of 12 points in the total GSRS score (15-105 scale) considering a 0.05 significance level and a standard deviation of 18 and allowing for a 20% dropout. A paired t test will be utilized to compare the overall GSRS score, the GSRS subscale scores, and the GIQLI from baseline.

- Assuming a 5% 1-year rate of acute rejection, we plan to evaluate 60 historical control patients to compare differences in the secondary endpoints of acute rejection, graft survival, patient survival, and infections. The historical control group will be randomly selected from a consecutive list of patients who received a renal transplant during the same study period and were maintained on MMF 500mg-1gram BID or EC-MPS 360-720mg BID, tacrolimus, and prednisone and met stated inclusion and exclusion criteria as listed below. 30 conversion patients will be enrolled and compared 1:2 with historical controls.
- Statistical analysis for the historical control comparison will utilize the Chi-squared test for events, ANOVA for renal function outcome differences and other continuous variables, and Kaplan-Meier estimates for patient and graft survival

Ethical considerations

Regulatory and ethical compliance

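### Controls transplanted during the study cannot already have completed follow-up; with no control time zero or minimum follow-up, crude rejection and infection proportions may rest on unequal observation

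*Combined protocol and SAP*

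**What the plan says.** Four parts of the combined protocol and SAP bear on who the controls are and how long they were observed.

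- **Sample size calculation:** 60 controls are to be "randomly selected from a consecutive list of patients who received a renal transplant during the same study period" and who "were maintained on MMF 500mg-1gram BID or EC-MPS 360-720mg BID, tacrolimus, and prednisone". They are compared 1:2 with 30 conversion patients. Events are compared by chi-squared test, and patient and graft survival are estimated by Kaplan-Meier.
- **Treatment arms:** the comparison is a retrospective one with patients on azathioprine (AZA), and "these patients have already been allocated treatment and completed follow-up".
- **Purpose and rationale:** the comparators are called a historic cohort. "They will be compared on a 2:1 basis to a group of randomly selected patients previously converted to AZA".
- **Study design, Population and Data analysis:** "This study will be conducted over a 2-year period, during which patients will be enrolled through the first year". A one-year minimum for follow-up is set, but only for enrolled patients. Those patients received their transplant "in the year prior to enrollment who are exhibiting signs of non-infectious GI toxicity". On the timing of the analysis, the plan states: "Statistical analysis and report writing will be performed when the last subject has completed 12 months on study".

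No section gives the controls calendar dates, a time zero, a minimum follow-up or a data cut-off.

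**The concern.** A patient transplanted during the study cannot have completed follow-up when the protocol was written, so whoever pulls the charts must break one of the two rules. The only study period the protocol defines is the 2-year one. On that literal reading, a control transplanted in month 18 has at most 6 months of observation at month 24.

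This matters because a chi-squared test on event counts ignores how long each patient was observed. Acute rejection and infections are both named control comparisons, and they inform the secondary objective of whether the switch is safe. Everolimus patients are counted over 12 months from enrollment; controls have no matching window. If controls with short follow-up are included, their crude proportions fall for a reason unrelated to treatment.

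**Working it through.** **Inputs from the plan.** One-year acute rejection 5%; 60 controls and 30 conversion patients (2 × 30 = 60, so the number of controls follows from the ratio; no power basis is stated for this comparison); study length 24 months; enrollment in months 0 to 12; analysis when the last subject reaches 12 months, about month 24. Everolimus patients can therefore have been transplanted in months -12 to 12.

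**Assumptions.** Control data are cut at month 24. Transplant dates are uniform over the window. The hazard is constant: λ = -ln(0.95)/12 = 0.00427 per month. Observation is capped at 12 months.

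**Formula.** Expected crude proportion = mean of 1 - exp(-λ × min(follow-up, 12)). With 12 full months for everyone this is 5.0%, or 0.05 × 60 = 3.0 events.

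**Time counted from transplant**

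1. *Window = all 24 months.* Half the controls (months 0 to 12) have a full 12 months and contribute 5.0%. The other half have follow-up uniform on 0 to 12 months and contribute 1 - 0.05/(12λ) = 1 - 0.05/0.0513 = 2.52%. The average is (5.0 + 2.52)/2 = 3.76%, or 2.3 events in 60. Mean capped follow-up is (12 + 6)/2 = 9.0 months.
2. *Same window, front-loaded rejection* (assume 60% of the 12-month events fall in the first 3 months and the rest evenly after). The short half contributes 0.25 × 1.5% + 0.75 × 4.0% = 3.375%. The average is (5.0 + 3.375)/2 = 4.19%, or 2.5 events in 60.
3. *Window = enrollment year (months 0 to 12), or months -12 to 12.* Every control has at least 12 months by month 24. The crude proportion is 5.0%, with no shortfall.

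**Time counted from a later, conversion-type index date** (assumed uniform over 0 to 12 months after transplant; constant hazard from that date)

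| Control transplant window | Share with under 12 months | Crude proportion | Events in 60 |
|---|---|---|---|
| Months 0 to 24* | 67% | 3.3% | 2.0 |
| Months 0 to 12 | 50% | 4.2% | 2.5 |
| Months -12 to 12 | 25% | 4.6% | 2.8 |

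*Leaves out the 25% whose index date would fall after month 24. Counting them as controls with no follow-up would give 75% short and 2.5%.

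Across these readings the shortfall for rejection runs from zero to 5.0 - 3.3 = 1.7 percentage points, about one event in 60. The plan gives no infection rate, so that endpoint cannot be sized.

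**The case against.** The strongest case against is that the shortfall rests on one reading of an undefined phrase. Read as the enrollment year, or as the window from which the everolimus patients themselves come, and counted from transplant, it leaves no control short. No section makes month 24 the control data cut-off. This stands, and it is why the shortfall can only be stated conditionally. It does not remove the contradiction, and a time zero closer to everolimus enrollment brings some of the shortfall back even with the narrower windows.

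A reader might infer that everolimus will look worse on safety, with an apparent relative risk of 5/3.76 = 1.33 when there is no true difference. The documents do not support that as a general conclusion. If the control clock starts at transplant, controls contribute early post-transplant time that everolimus patients, followed from enrollment up to a year later, do not. If rejection is front-loaded, that raises the control rate and works the other way. Front-loading also cuts the truncation effect by itself to 5/4.19 = 1.19.

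A reader might also infer that all the safety comparisons are understated. Kaplan-Meier allows for censoring in patient and graft survival, so the concern is confined to crude proportions.

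A further tempting step is to say that concurrent controls are largely patients who declined or were not approached. Enrollment closes after the first year, so on the 24-month reading the half transplanted in months 12 to 24 could not have been enrolled. The documents do not support saying largely.

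Finally, the effect is small beside the noise. The exact 95% interval for 3 events in 60 is about 1.0% to 13.9%. With true rates of 5% (n = 30) and 3.76% (n = 60), the uncorrected chi-squared test rejects at the 0.05 level in 6.4% of trials, against 3.6% when both are 5%; with continuity correction the figures are 1.1% and 0.6%. That is fair, and it limits the weight of the point.

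**Conclusion.** The contradiction holds: the study-period rule conflicts with completed follow-up and with the description of a historic cohort, and nothing in the plan sets a control time zero or minimum follow-up. It is more than a missing detail, because the two rules exclude each other and the literal 2-year reading puts unequal follow-up into a test on counts.

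The numerical consequence is conditional. On the 2-year reading, with data cut at about month 24 and time from transplant, up to half the controls could have under 12 months, and the expected crude rejection proportion is about 3.8% (constant hazard) or 4.2% (front-loaded) rather than 5%. On the narrower windows, counted from transplant, it is zero. The net direction of bias in the comparison with everolimus is not determined until the control time zero is fixed. This is a modest issue in a secondary safety comparison, and one that should be corrected.

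The same control sentence carries a separate conflict: it describes patients maintained on MMF or EC-MPS, whereas the Purpose and rationale and Treatment arms sections describe patients on AZA. Settling that would not by itself define the window, but the choice of time zero depends on it.

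**What to change.** Before charts are selected, amend the plan as follows.

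1. Reconcile Purpose and rationale, Treatment arms and Sample size calculation on which cohort is the control group and on one calendar window with stated dates.
2. Define a control time zero comparable to everolimus enrollment: for example, a date matched on time since transplant or, if the controls are AZA patients, the conversion date. Patients maintained on MMF or EC-MPS have no conversion date, so for them a matched date would be needed.
3. Require each control's time zero to fall at least 12 months before data extraction. Make this a rule about the opportunity to be observed, so that patients who died or lost the graft within the 12 months stay in.
4. For the chi-squared tests, count rejection and infection over the same 12-month window in both groups.

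The cost is protocol wording, with the same 60 charts. Taking controls from an earlier calendar era is one way to meet the third item but is not required. It gives up same-era practice, and if chosen the difference in era should be stated as a limitation.

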Study drug discontinuation	Point/time when patient permanently stops taking study drug for any reason; may or may not also be the point/time of premature patient withdrawal
Variable	Information used in the data analysis; derived directly or indirectly from data collected using specified assessments at specified timepoints

Protocol synopsis

Title of study: Conversion from MPA to Zortress (everolimus) for GI toxicity post-renal transplantation

This study is a prospective, single-center study to evaluate the effectiveness of conversion from MMF or EC-MPS to EVR during the first year post-renal transplant in patients who experience gastrointestinal adverse effects. The primary outcome will be change in GSRS from baseline (time of conversion) to 30 days post-conversion.

In total, 25 patients will be enrolled and converted from MPA to EVR, at an initial dose of 1 mg PO BID with target everolimus troughs between 3 - 8 ng/mL. Patients who are less than one year from date of transplant with identified GI symptoms who are on immunosuppression with tacrolimus, MPA, and prednisone will be enrolled and followed for 1 year. These patients will be compared to an historical cohort of patients receiving azathioprine for safety outcomes (including rejection and graft/patient survival).

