- 2. Presence of a preexisting significant GI condition that does not have a presumed causal relationship with MPA

- 3. Evidence of any GI disorder induced by an infection, underlying medical condition, or concomitant medication other than MPA
- 4. eGFR<35 ml/min at time of possible conversion
- 5. Proteinuria >1 gram/day at time of possible conversion
- 6. Profound bone marrow suppression at the time of possible conversion as defined as:
 - Hemoglobin <10 g/dL
 - WBC <3 K/cumm
 - Platelets <100 K/cumm
- 7. Wound healing issues at time of possible conversion (eg, wound dehiscence, wound infection, incisional hernia, lymphocele, seroma)
- 8. Elevated total cholesterol (>350 mg/dL) and/or triglycerides (>500 ng/dL) at time of possible conversion
- 9. Hypersensitivity to everolimus, sirolimus, or other rapamycin deriviatives

Investigational and reference therapy:

Investigational therapy

- Everolimus tablets 0.25 mg, 0.5 mg, and/or 0.75 mg

Study design: Patients will be selected if they experience non-infectious GI adverse effects within the first 12 months post transplant. Following selection they will have a baseline screening and enrollment with a complete medical history, medication history, vital signs and labs (including tacrolimus and everolimus levels). In addition, their adverse effects and GSRS and GIQLI will be recorded. After enrollment they will have medication history, vitals, labs (including tacrolimus), and GSRS/GIQLI and adverse events recorded at months 1, 3, 6, 9, and 12 (excepting GSRS and GIQLI at month 9).

Efficacy assessments:

- Change in GSRS from baseline to month 3
- Change in GSRS subscores from baseline to month 3
- Changes in GSRS from basline to month 6 and 12
- Change in GIQLI from baseline to month 3
- Change in GIQLI subscores from baseline to month 3
- Changes in GIQLI from baseline to month 6 and 12

Other assessments:

- BPAR rates during study (compared with historical control)
- eGFR by MDRD4 from baseline to month 12 (compared to historical control)
- Death (compared with historical control)
- Graft loss (compared with historical control)

Data analysis:

Data for primary and secondary efficacy will be compared using a paired T-test.

Background

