Cellcept® (mycophenolate mofetil, MMF) and Myfortic® (enteric-coated mycophenolate sodium, EC-MPS) are the two formulations of mycophenolic acid (MPA) approved for use as adjunctive immunosuppression post-renal transplantation. Non-infectious gastrointestinal (GI) adverse effects are the main dose-limiting toxicity of MPA therapy, which has been reported in up to 45% of MPA-treated patients. MPA dose reductions, treatment interruptions, discontinuations or withdrawals are common due to GI toxicity from these agents. Studies have demonstrated that patients with GI complications who experienced an MMF dose adjustment or discontinuation had a significantly increased incidence of acute rejections compared with patients without GI complications (30.2% vs. 19.4%, p=0.005). At Barnes-Jewish Hospital/Washington University School of Medicine in St. Louis, it is standard practice to place patients on triple maintenance immunosuppression therapy with MMF or EC-MPS, tacrolimus, and prednisone immediately post-renal transplantation. Patients may be switched from MMF or EC-MPS to azathioprine due to GI symptoms. We feel that everolimus (EVR) may offer a similar advantage to azathioprine for patients unable to tolerate MMF or EC-MPS in regard to similar incidence of acute rejection, low incidence of GI-related adverse effects, and other patient-oriented outcomes.

Purpose and rationale

This study is a prospective, single-center, single-arm study to evaluate the effectiveness of conversion from MMF or EC-MPS to EVR during the first year post-renal transplant in patients who experience gastrointestinal adverse effects. The secondary outcomes will include a comparison of EVR-based immunosuppression to azathioprine (AZA)-based immunosuppression, which is the current standard of practice at this institution. It is felt that EVR-based immunosuppression may offer certain advantages over AZA, including the ability to use lower-exposure tacrolimus maintenance and preserve kidney function as compared to AZA or MPA.

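### The single historical control group is defined as azathioprine patients in most of the protocol, but as patients kept on mycophenolate in the Sample size section that selects it

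*Combined protocol and SAP*

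**What the plan says.** All references are to the combined protocol and SAP.

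**AZA as the comparator**
- Protocol synopsis: "These patients will be compared to an historical cohort of patients receiving azathioprine for safety outcomes".
- Purpose and rationale: the secondary outcomes include a "comparison of EVR-based immunosuppression to azathioprine (AZA)-based immunosuppression, which is the current standard of practice at this institution". This sentence does not call the comparator historical.
- Purpose and rationale, later: the outcome data are set against "an historic cohort of patients who were converted to AZA for GI adverse effects". It adds: "They will be compared on a 2:1 basis to a group of randomly selected patients previously converted to AZA".
- Treatment arms: a retrospective analysis of patients on AZA-based immunosuppression, whose treatment is already allocated and whose follow-up is finished.

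**MPA as the comparator**
- Sample size calculation (10.6 in the table of contents): 60 historical controls, 1:2 against 30 conversion patients. They are sampled at random from recipients transplanted in the same period as the study who "were maintained on MMF 500mg-1gram BID or EC-MPS 360-720mg BID, tacrolimus, and prednisone and met stated inclusion and exclusion criteria as listed below".

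The synopsis list of other assessments refers to a historical control without defining it, for example "eGFR by MDRD4 from baseline to month 12 (compared to historical control".

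**The concern.** A patient kept on MMF or EC-MPS is not a patient converted from it to AZA. Someone who builds the control list from the Sample size section, the only place with an operational sampling rule, would therefore assemble a different population from the one described elsewhere.

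Safety is the only secondary objective, and this is its only external comparison. With AZA controls it asks how everolimus performs against the institution's usual alternative after MPA intolerance. With MPA controls it asks how switching to everolimus performs against not switching. A result from one does not answer the other.

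The study is open-label, analysts included, and analysis waits until the last subject has completed 12 months. The plan does not say when controls are chosen. If the conflict stays open, the comparator could be settled after the everolimus outcomes are known.

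**Working it through.** **1. One group or two?** The plan's own count reproduces: 30 conversion patients × 2 = 60 controls. The 2:1 in Purpose and rationale and the 1:2 in Sample size calculation are the same ratio. Both descriptions use random selection, and both cover rejection, graft survival and patient survival. No section plans a second cohort. The count is ratio arithmetic and is the same under either definition, so the conflict lies in the definition and not in the number.

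**2. The two definitions side by side**

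| Feature | Synopsis, Purpose and rationale, Treatment arms | Sample size calculation |
|---|---|---|
| Regimen | AZA, after conversion for GI effects | MMF or EC-MPS, maintained |
| AZA mentioned | Yes | No |
| Timing | Previously converted, follow-up finished | Transplanted during the study period |
| Time zero for follow-up | Not named | Not named |
| Eligibility | GI adverse effects leading to conversion | Trial criteria, said to follow the sentence, but none do |

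**3. Timing within the Sample size section.** It calls the controls historical, yet takes them from the period of the study. Study design states: "This study will be conducted over a 2-year period, during which patients will be enrolled through the first year". The section does not say whether its period means the two years, the enrolment year, or the window in which the everolimus patients were transplanted.

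**4. Time zero.** The Renal Function section follows eGFR in the everolimus arm from enrolment to month 12. AZA conversion would be a natural matching date, but no section names it. For MPA-maintained controls, exclusion criteria 4 to 8 (eGFR, proteinuria, marrow suppression, wound healing, lipids) are judged when conversion is being considered. That is a possible anchor, but it is not named as time zero either.

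**5. The 5% rejection rate.** It is assigned to neither definition, and no target difference or power is given with it. At 5% the expected rejections are 30 × 0.05 = 1.5 and 60 × 0.05 = 3.0.

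**6. What the comparison can detect (context only).** With 5% in 60 controls, a two-sided 0.05 level and exact enumeration of the chi-squared test, power depends on the everolimus rate. The documents give no such rate, so the first column is assumed.

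| Assumed everolimus rate | Power, uncorrected | Power, continuity-corrected |
|---|---|---|
| 10% | 15.3% | 6.7% |
| 20% | 60% | 44% |
| 25% | 78% | 66% |

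With 5% in both groups, the Wald 95% half-width for the difference is 1.96 × √(0.05 × 0.95 × (1/30 + 1/60)) = 1.96 × 0.0487 ≈ 9.6 percentage points. This is a rough guide at so few events. None of these figures shows which control group is meant.

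**The case against.** **A charitable reading.** The Sample size sentence might describe the regimen before conversion to AZA, because controls must also meet the trial criteria, which include GI toxicity from MPA. The wording does not support this: it says patients were maintained on MPA and mentions neither AZA nor conversion. Even if that was the intent, a chart abstractor could not tell, so the text would still need changing.

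**MPA as a legitimate benchmark.** Purpose and rationale does mention MPA when discussing kidney function and rejection. Only the Sample size section, however, turns MPA patients into a control cohort.

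**Limited reach.** This stands. The primary GSRS analysis and the within-arm safety summaries do not use the controls.

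A reader might also infer more than the documents support:
- *That MPA-maintained controls are self-contradictory, since they must have MPA toxicity yet stay on MPA.* They are not. The Background says dose reductions are common and that patients may be switched. The population is coherent, but it is a different one.
- *That such controls cannot have a baseline, because baseline means conversion.* The synopsis phrase "change in GSRS from baseline (time of conversion" concerns the GSRS. For eGFR the protocol starts at enrolment, and the exclusion criteria offer a possible anchor. What holds is that no control time zero is named under either definition.
- *That the Treatment arms statement about finished follow-up directly contradicts sampling during the study period.* That statement is about AZA patients, so this mostly restates the main conflict. The separate tension is inside the Sample size section, between historical controls and a concurrent transplant period.
- *That low power makes the definition unimportant.* Power ranges widely with the assumed rate, and even a descriptive comparison needs one stated population and start date.

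**Conclusion.** The plan contradicts itself on who the historical controls are. Three sections (Protocol synopsis, Purpose and rationale, Treatment arms) specify AZA patients; the Sample size section specifies MPA-maintained patients for the same group of 60. The sampling rule cannot be carried out in a way that satisfies both, and the choice changes the safety question being answered. The undefined time zero, the unclear period, the criteria pointer that leads nowhere and the unassigned 5% rate are secondary gaps in the same paragraph.

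The finding rests on the text and needs no assumption about event rates. The size and direction of any effect on those rates cannot be derived from the documents. AZA conversion is the better-supported reading, but the documents do not establish that it was intended. The correction is needed before the control cohort is drawn.

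**What to change.** Before any control charts are selected, reconcile the Sample size section with the Protocol synopsis, Purpose and rationale, and Treatment arms sections. The sponsor should state one comparator. If the sponsor confirms AZA:

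1. Replace the control-selection sentence with, in substance: controls are a random sample from a complete sequential list of recipients converted from MMF or EC-MPS to azathioprine because of GI toxicity, who at conversion met the protocol's clinical inclusion and exclusion criteria (all except study consent).
2. Set time zero at the AZA conversion date. Assess the planned control endpoints (acute and chronic rejection, graft loss, death, infection, eGFR) over the following 12 months, as for everolimus.
3. Replace the reference to the study period with calendar dates that allow 12 months of potential follow-up, without requiring survival to 12 months.
4. State which group the 5% rejection rate describes.
5. Point the eligibility reference to the protocol's Inclusion criteria and Exclusion criteria sections.

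If the sponsor instead confirms MPA-maintained controls, the other three sections need changing, and a time zero must be defined for patients who never converted.

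The cost is a wording amendment before chart review. Fewer than 60 AZA conversions may qualify, in which case the control count must be restated. Controls from earlier years may differ in era of care, which should be declared as a limitation.
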